procedures based on external tattoos and room lasers. A free- breathing trace of the Calypso transponders will be obtained to allow the patient to settle on the treatment table and to study real-time respiratory traces. The patient will then be asked to perform a therapist-coached modified slow vital capacity maneuver and DIBH maneuver [1] and hold their breath. Patients will have the ability to perform this maneuver with or without biofeedback from digital goggles that are placed over the patient's eyes and display the breathing trace of the Calypso transponders. The use of the digital goggles will be determined by patient preference or at the discretion of the treatment team. This will allow us to investigate whether real-time biofeedback adds to the reproducibility of patients holding their breath. A DIBH cone-beam CT will be acquired in approximately three breath-holds, once a week for standard fractionated RT patients or with each fraction for SBRT patients. After review and approval of the images, the patient will be treated while holding their breath using the DIBH maneuver. In standard fractionated RT patients the radiation treatment will be guided by the external tattoos and daily 2D kV imaging. The Calypso transponder signal will be used to monitor the level of the breath-hold during treatment. The breath-hold level based on the Calypso transponder signal will be verified daily by the 2D imaging and once a week in 3D by the DIBH cone-beam CT. In SBRT patients, the radiation treatment will be guided by the external tattoos and daily DIBH cone-beam CT. The Calypso transponder signal will be used to monitor the level of the breath-hold during treatment. The therapists will monitor the respiratory trace signal from the Calypso transponders throughout the treatment and will initiate the radiation treatment delivery when the patient holds his/her breath within the tolerance level the patient has been assigned to. This will be continued up until the initially planned 30 patients are accrued.. Should the transponder signal indicate that the target has moved outside of the preset tolerance, the therapists will hold further radiation treatment delivery until the patient's breathhold has returned to the desired target range or until the patient's setup has been corrected. In the additional 25 patients planned, the margins will be reduced in a step-wise fashion. The gate will be decreased 1mm per each set of 5 patients until the duty cycle (beam-on time) and number of DIBH attempts are doubled. The gate at which this occurs will be considered the minimum clinically feasible gate

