Locally-advanced NSCLC patients receive fractionated RT, ideally 60 Gy in 30 fractions when given with concurrent chemotherapy.[12-14] Frequently, the predicted toxicity from radiation dose to the lungs and spinal cord using widely agreed upon dose constraints to these organs limit our ability to treat patients to the optimal prescription dose. [15, 16] Respiratory motion can significantly increase the treated volume, especially in patients with already large tumors. The most common toxicities in this patient population are esophagitis and respiratory toxicity including radiation pneumonitis.[14, 17] The same challenges exist for patients with limited-stage small cell lung cancer treated with chemotherapy and thoracic radiation therapy.[18-20] Techniques to address intrafraction tumor motion include abdominal compression, respiratory gating, and active breathing control (ABC).[21] While these are all clinically approved techniques, they are not currently widely used in practice. Abdominal compression can be uncomfortable to the patients and does not necessarily control internal motion well.[22] In addition, it compresses the lungs and does not consistently improve sparing of normal tissues, but may actually worsen the dosimetry.[23] Respiratory gating based on external markers can be misleading due to the potential discrepancy between external marker and true internal target motion.[24, 25] ABC is an involved process using a spirometer which is frequently uncomfortable to the patient, and there are problems with changes in tidal volume, volume expansion, patients' response and adaptation to the system.[26, 27] These techniques all depend on unreliable surrogates of the target position, and frequently cannot be tolerated by patients because of patient discomfort or are too complex for patients to manage, making them far from ideal .

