In the additional 25 patients to be accrued the window will be reduced in a step-wise fashion by 1mm for every 5 patients. Number of beam holds, treatment interruptions and total treatment time from first beam-on time to the last beam-off time will be recorded by the therapists.

If a patient cannot achieve the desired breath hold after 3 attempts and discussion with the therapist, the therapist can treat with the best breath-hold achievable and report the change in level to the treating physician. Additionally, the therapist will acquire an orthogonal pair of images. The physicist will then estimate the dosimetric effects per day in case the patient is still unable to achieve adequate breath hold the next day. Depending on the estimated dosimetry and the patient's reasons for not being able to achieve breath hold, the patient may be taken off protocol if unable to perform the breath hold to within +/- 5 mm for 3 consecutive treatment days. Patients who are taken off protocol prior to treatment completion will be treated based on the free-breathing treatment planning scan for the remainder of the radiation treatment course.

9.1 For patients undergoing SBRT in 10 or less fractions, the following procedures will be performed:

1. Standard setup procedures based on external tattoos will be performed.
2. The Calypso antenna will be deployed and positioned over the patient's chest. Tracking of the Calypso transponder signal will commence.

3. For patients who have been selected to use the digital goggles, the DIBH maneuver will be performed with visual biofeedback at least once a week and at least one fraction will be done without visual feedback. During treatment the radiation therapist will coach the patient on how to hold their breath during the treatment. On treatment days with visual feedback, the patient will be able to view and control his/her breathing through biofeedback using goggles (Myvu Personal Media Viewer, Myvu Corporation) or an iPhone that displays the Calypso trace. The couch position will be adjusted by the therapists in the treatment room to accurately set up the patient for treatment in DIBH based on the Calypso signal. The Calypso trace will be set to zero based on the DIBH level.
4. The patient will resume regular breathing and the therapists will leave the room.

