5. The patient will be remotely asked to repeat the DIBH maneuver and a CBCT will be obtained over several breathholds (exact number depending on the patient's ability to hold their breath) using partial arcs and the assigned breath hold tolerance window.
6. The CBCT images will be evaluated and the patient will be repositioned for a soft tissue match as needed. The soft tissue match will then be evaluated and approved by the treating physician as is our normal clinical process. The isocenter coordinates in Calypso will be changed based on the patient's repositioning shift dictated by the CBCT soft tissue match. No more than 2 CBCTs per treatment will be done for protocol purposes.

The patient will then be remotely asked to reproduce the DIBH maneuver with the tolerance window to which they have been assigned and be treated in DIBH. Number of beam holds, treatment interruptions and total treatment time from first beam-on time to the last beam-off time will be recorded by the therapists. Beacon position during DIBH will be monitored by the therapist to assure that the patient maintains the DIBH position throughout the treatment delivery. If the Calypso beacon signal indicates that the tumor has moved outside of the tolerance window, the radiation beam will be automatically held by the system and resumed when the target is within range.

9.2 For patients undergoing standard fractionated RT the following procedures will be performed:

1. Standard setup procedures based on external tattoos will be performed.
2. The Calypso antenna will be deployed and positioned over the patient's chest. Tracking of the Calypso transponder signal will commence.

Optional: In patients where the Calypso antenna external markers detected by an in-house infrared tracking system can be arranged in such a way that both signals can be obtained

simultaneously (depending on body habitus), a free-breathing trace of the Calypso transponders over 2 minutes in combination with the external marker signal will be obtained . These will be used for future analysis and building of an external/internal respiration model.

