Reproducibility of using internal tumor surrogates (Calypso beacons) during repeated deep inspiration breath hold maneuvers with and without visual biofeedback will be evaluated by posthoc analysis of the Calypso signal traces. The ability to maintain the breathhold to within the tolerance level to which they have been assigned will be assessed. Number of beam holds and treatment interruptions will be recorded as an objective measure of the patient's ability to maintain their breathhold. Whether or not visual biofeedback will aid in the ability to hold their breath reliably and within the target region will be assessed using the number of treatment interruptions. We will also assess differences in duty cycle and number of DIBH attempts with and without visual biofeedback. Differences in the ability of maintaining the DIBH maneuver within the gate with and without visual biofeedback will be measured as duty cycle, a quantifiable measure of how long it takes to deliver a radiation treatment. It is related to how well patients can hold their breath and the tumor in the target position. Each patient will have the goggles 50% of the treatments and without goggles the other 50% of the time. Wilcoxon rank sum tests will be done to compare the duty cycle.

The residual intrafraction motion and drift during DIBH will be determined based on the Calypso signal traces which may provide critical insight into the ability to immobilize the tumor by DIBH. Beacon position stability will be determined on acquired cone-beam CTs by measuring the distance of the beacons to the center of the gross target volume {GTV} as well as the distance of the beacons to each other. Improvement of normal tissue dosimetry based on Calypso-guided DIBH will be determined from the treatment plans developed on the free-breathing and DIBH simulation CT scans. Specific dosimetric parameters will include the chest wall V30, total lung V20, mean lung dose, lung toxicity model metrics (Lyman model NTCP and parallel model fraction damaged (fdam)), mean and maximum esophageal dose, and maximum spinal cord dose.

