For the 1st secondary objective, we will compare the visual vs no visual biofeedback treatments (for patients who agree to use the digital goggles) by the number of treatment interruptions. We expect that there will be fewer treatment interruptions when using biofeedback. To this end Wilcoxon signed-rank tests will be conducted based on the patients who can successfully be treated.

For the 2nd secondary objective, we will assess differences in the ability of maintaining the DIBH maneuver within the fate with and without visual biofeedback. Such differences will be measured as duty cycle, and will be compared using Wilcoxon signed-rank tests based on the patients who can successfully be treated.

For the 3rd secondary objective, the residual intrafraction tumor motion (surrogated by Calypso) will be measured in all 3 dimensions and the euclidean distance will be calculated, which will then be correlated with the normal tissue dosimetry (see end of Section 12.0). Patients will receive multiple fractions and thus multiple measurements of such distance will be obtained from the same patients.

These repeated measures will be averaged for each patient and the correlation will be examined by simple linear regression. If such continuous data are skewed, we may either use an appropriate monotone transformation, or examine the nonparametric correlation coefficient (such as Spearman rank correlation coefficient) between the tumor motion and the normal tissue dosimetry instead.

For the 4th secondary objective, the potential increase in dose escalation and decrease in margins made possible by Calypso- guided DIBH, as contrasted to those obtained from the 40 CT scan, will be formulated as pair data from each patient and tested by using Wilcoxon signed-rank tests. Dosimetric parameters listed at the end of Section 12.0 will be used again for such analysis.

The 5th secondary objective does not require statistical analysis. See Section 12.0 for details.

For the 6th secondary objective, tumor shrinkage, beacon position and centroid changes in conventionally fractionated patients (totally 10), all measured as continuous variables, will be summarized descriptively.

For the 7th secondary objective, intra- and inter-fraction variation in lung volume preservation of multiple DIBH maneuvers will be recorded within each patient and summarized descriptively.

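### The first biofeedback comparison uses a count of treatment interruptions with no per-fraction denominator, so it is fair only if goggles and no-goggles fractions are kept near equal, as Section 12 says but Section 9 does not require

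*Combined protocol and SAP*

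**What the plan says.** Section 14 (first secondary objective) compares visual with no visual biofeedback, in patients who agree to wear the goggles, "by the number of treatment interruptions. We expect that there will be fewer treatment interruptions when using biofeedback". The test is a Wilcoxon signed-rank test in patients who can be treated successfully. Section 12 names the same number of interruptions as the measure. Neither section divides it by fractions or by treatment time.

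Three places bear on how many fractions fall in each condition:

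- Sections 9.1 (SBRT) and 9.2 (standard fractionation): for patients selected to use goggles, the breath-hold is done "with visual biofeedback at least once a week and at least one fraction will be done without visual feedback".
- Section 12: "Each patient will have the goggles 50% of the treatments and without goggles the other 50% of the time".
- Section 1: goggles use follows patient preference or the treatment team's discretion.

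On recording, Section 9 says that the number of beam holds, "treatment interruptions and total treatment time from first beam-on time to the last beam-off time will be recorded by the therapists". No section asks for goggles use to be noted at each fraction.

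**The concern.** A total count grows with the number of fractions over which it is collected. If one condition has more fractions, its total is larger even when biofeedback does nothing. Pairing within patient does not remove this, because the imbalance lies inside each patient.

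At the weekly goggles minimum the error runs in the direction that Section 14 expects, so it would be easy to accept without question. At the opposite extreme it would hide a real benefit. Section 1 presents the biofeedback question as something the study will answer, so the count should not depend on how often the goggles happened to be worn.

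**Working it through.** The plan gives no power, effect size or error rate for this comparison, so there is no figure to reproduce. The check asks what the permitted schedules do to a raw total.

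**Inputs.** A standard course is "ideally 60 Gy in 30 fractions when given with concurrent chemotherapy" (Section 3.1). Five fractions a week is assumed. SBRT is 10 or fewer fractions (Section 9.1), and a 5-fraction course in one week is assumed as the example. The documents give no interruption rate or goggles uptake, so 0.5, 1 and 2 interruptions per fraction and 10 or 25 patients are assumed.

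**Arithmetic.** With the same rate λ per fraction in both conditions, g goggles fractions and c no-goggles fractions, the expected totals are gλ and cλ. Their ratio is c/g whatever λ is.

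- Standard course: 30/5 = 6 weeks. The Section 9 goggles minimum gives g = 6, c = 24 and c/g = 4. Goggles could triple the rate (6 × 3 = 18, against 24) and still show the smaller total.
- The other extreme allowed by Section 9 is g = 29, c = 1. Goggles would have to cut the rate to 1/29 of the no-goggles rate for the totals to be equal.
- Equal split under Section 12: g = c = 15 and the ratio is 1.
- Five-fraction SBRT under an equal-split rule: 2 and 3, ratio 3/2 = 1.5, in one direction or the other.

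**Simulation.** No goggles effect; Poisson counts; patient rates from a gamma distribution with coefficient of variation 1; two-sided 5% signed-rank test; 2,000 trials per setting; every patient given the same split. Ranges run over the three assumed rates and both patient numbers.

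| Goggles / no goggles | Raw totals: false rejection | Per-fraction values: false rejection |
|---|---|---|
| 15 / 15 | 4–5% | 4–5% |
| 6 / 24 | 99–100%, favouring goggles | 4–5% |
| 29 / 1 | 100%, against goggles | 5–14% |
| 2 / 3 (n = 10) | 12–36% | 4–5% |
| 2 / 3 (n = 25) | 31–79% | 5% |
| 1 / 4 | 63–100%, favouring goggles | 5–6% |

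The 2/3 rows need every patient to have the extra fraction in the same condition. When patients alternate between 2/3 and 3/2, raw totals reject in about 1–5%.

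**With a true effect** (25 patients, 1 interruption per fraction):

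- Goggles 50% worse at 6/24: raw totals favour goggles in 100% of trials, while the per-fraction test correctly goes against them in 96%.
- Goggles 30% better: the per-fraction test detects this in 96% of trials at 15/15, 82% at 24/6 and 12% at 29/1. Raw totals point the wrong way in 100% at both 24/6 and 29/1.

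The denominator therefore removes the bias, but a very uneven split still costs power and some error control.

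**The case against.** The strongest reply is that Sections 9 and 12 do not conflict. Section 9 sets floors and Section 12 sets the allocation, and an equal split meets both. If it is followed on even courses, raw totals are fair. This stands, and it makes the finding conditional. A reader might infer that the plan prescribes an invalid test, or that a near-certain false positive awaits. The documents do not support that, because the figures near 100% require delivery to follow only the Section 9 minimums, with patients leaning the same way. What remains is that staff work from the Section 9 steps, which do not carry the equal split, and Section 1 leaves use to preference or discretion.

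A second reply is that a per-treatment mean is a natural reading. Counts are recorded session by session, and for the third objective Section 14 averages repeated measures within patient. That is fair: the gap is an unstated denominator, not a declared wrong one. Section 14 states the averaging for one objective and not for this one.

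Two other stronger readings also fail. The bias does not always flatter goggles, since it reverses at 29/1. Odd SBRT courses are not biased in themselves; they matter only if the extra fraction consistently falls in the same condition, and no document says that it does.

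It is also true that beam holds and treatment interruptions are listed together in Section 12 ("Number of beam holds and treatment interruptions will be recorded as an objective measure of the patient's ability to maintain their breathhold") without being told apart, and that Section 1 has therapists holding the beam where Sections 4.2 and 9 describe an automatic hold. These are matters of clarity. They do not show that events were or will be recorded with bias.

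**Conclusion.** The concern holds in conditional form. The first biofeedback test has no stated denominator, and the delivery steps allow fraction numbers unequal enough to decide the result. Under the Section 12 equal split on even courses there is no problem. At the Section 9 goggles minimum the totals differ 4-fold with no goggles effect. That ratio rests only on the 30-fraction course and the assumed five fractions a week. The rejection rates also rest on assumed interruption rates, assumed patient numbers and a common direction of imbalance across patients.

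The change is worth making because it costs almost nothing and removes the dependence on which section was followed. The consequence is limited to one secondary objective. The primary feasibility test, the sample size, the stopping rules and the duty-cycle comparison are unaffected.

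**What to change.** 1. **Section 14.** For each patient and condition, divide the number of interruptions by the number of fractions delivered in that condition, and apply the planned signed-rank test to the paired per-fraction values.
2. **Sections 9.1 and 9.2.** Repeat the Section 12 equal split. Courses with an odd number of fractions differ by one; alternate across patients which condition gets the extra fraction. Record goggles yes or no at every fraction.

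The two steps belong together. The per-fraction test holds about 4–7% error at moderate splits but can drift to about 5–14% at extremes such as 29/1, where power is also poor.

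Optional clarifications: define a treatment interruption and say whether an automatic beam hold counts as one, after confirming what therapists actually log; and align the Section 1 wording on who holds the beam with Sections 4.2 and 9.

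Cost: one sentence in Section 14, one in each of 9.1 and 9.2, and one extra item per fraction on the treatment record. No new patient procedure is needed and the sample size does not change. The downside is slightly less freedom for a patient who dislikes the goggles. For patients already treated, check whether goggles use per fraction can be recovered. If it cannot, leave them out of this comparison and say so.

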2.0 OBJECTIVES AND SCIENTIFIC AIMS

Primary objectives:

- To evaluate the feasibility of using internal tumor surrogates (Calypso beacons) during repeated deep inspiration breath hold maneuvers for DIBH radiation treatments.

Secondary objectives:

- To compare the reproducibility with visual versus without visual biofeedback.
- To assess differences in the ability of maintaining the DIBH maneuver within the gate with and without visual biofeedback
- To measure the residual intrafraction tumor motion and associated improvement in normal tissue dosimetry during DIBH based on the Calypso lung transponder signal as a surrogate
- To measure the increase in dose escalation and the potential for decreasing margins made possible by Calypso-guided DIBH
- To determine the minimum clinically feasible gate margin for radiation
- To assess tumor shrinkage, beacon position and centroid changes in conventionally fractionated patients
- To assess intra- and inter-fraction variation in lung volume preservation of multiple DIBH maneuvers

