The patient will then be remotely asked to reproduce the DIBH maneuver with a tolerance window to which they have been assigned and be treated in DIBH Number of beam holds, treatment interruptions and total treatment time from first beam-on time to the last beam-off time will be recorded by the therapists. Beacon position during DIBH will be monitored by the therapist to assure that the patient maintains the DIBH position throughout the treatment delivery. If the Calypso beacon signal indicates that the tumor has moved outside of the tolerance window, the radiation beam will be automatically held by the system and resumed when the target is within range. For treatments between CBCT sessions, the patient will be set up according to steps 1-4, kV images will be acquired (Step 5) to verify beacon stability and the day's treatment with breath-hold will proceed without further imaging.

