To determine the minimum clinically feasible gate margins we will decrease the gate in a step-wise progression as far as a minimum of 2 mm. The gate will be reduced from +/- 5mm by 1mm for every 5 patients treated. Halving of the duty cycle will be considered the minimum gate that is clinically feasible. Once the minimum gate is determined, the remaining patients will be treated at +1mm from this value.

In the additional 10 conventionally fractionated patients, tumor shrinkage will be summarized as relative shrinkage in a percentage. Beacon position and centroid are 3D coordinates that will be determined as a distance from a landmark such as a bone or the carina.

Lung volume preservation will be assessed on wide field of view cone-beam CTs and compared intra- and interfraction within each patient to check for reproducibility or variability of lung volumes across multiple DIBH maneuvers.

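### Keeping the breath-hold within the gate is formally tested only as an undefined duty cycle, which on its most natural reading mixes gate-keeping with rest and other non-hold time

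*Combined protocol and SAP*

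**What the plan says.** Section 2.0 lists the objective: "To assess differences in the ability of maintaining the DIBH maneuver within the gate with and without visual biofeedback". Section 14.0 tests it through one variable: "Such differences will be measured as duty cycle, and will be compared using Wilcoxon signed-rank tests".

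Duty cycle is never given as a formula. The combined protocol and SAP describes it in three places:

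- Section 12.0 calls it "a quantifiable measure of how long it takes to deliver a radiation treatment" and adds: "It is related to how well patients can hold their breath and the tumor in the target position".
- Section 1.0, on narrowing the gate, treats it as beam-on time that rises: "until the duty cycle (beam-on time) and number of DIBH attempts are doubled".
- Section 12.0, on the same narrowing, has it falling: "Halving of the duty cycle will be considered the minimum gate that is clinically feasible".

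The treatment interval that therapists note is stated in Section 9.0 and again in 9.1 and 9.2: "total treatment time from first beam-on time to the last beam-off time will be recorded by the therapists". No section names it as the denominator of duty cycle, and none limits the denominator to time in breath-hold.

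The two sections also name different tests for duty cycle: the paired signed-rank test in 14.0 and the unpaired rank sum test in 12.0. The Calypso signal is recorded during treatment (table in Section 10.0), and Section 12.0 plans post hoc analysis of the traces but names no trace measure for this objective.

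**The concern.** Whether a patient stays inside the assigned tolerance window can be seen only while a breath-hold is in progress. A delivery-time measure over the whole beam-on to beam-off interval also reflects how long the patient rests between holds and any other pause. Goggles might change those pauses without changing gate-keeping, or improve gate-keeping while longer pauses hide it. The test would then answer a question about delivery efficiency, while the objective asks about gate maintenance.

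The design does not rule out such a difference. Goggle use follows patient preference or team discretion (Section 1.0), and nothing is randomized (Section 15.2). The share of fractions with goggles also differs between sections. Sections 9.1 and 9.2 ask for at least weekly use and at least one fraction without, while Section 12.0 gives an even split.

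**Working it through.** The plan states no effect size, SD, alpha or power for this comparison, so there is no figure to reproduce.

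**Inputs.** Hold length H = 20 s is the threshold in the eligibility criterion (Section 6.1). Rest per hold R, in-window fraction of hold time q, and all noise terms are assumptions.

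**Formula.** If the beam is on whenever the target is in the window during a hold, and the denominator is the recorded interval:

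- duty cycle D = qH / (H + R)
- in-window fraction = q, whatever R is.

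**Same patient, equal rest in both conditions.** The ratio of duty cycles is q1/q0, so the comparison has the right direction and relative size.

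**Same patient, same q, longer rest with goggles.** The ratio of duty cycles is (H + R) / (H + kR), where k is the ratio of rests.

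| Usual rest | k = 1.1 | k = 1.3 |
|---|---|---|
| 10 s | 30/31 = 0.97 | 30/33 = 0.91 |
| 30 s | 50/53 = 0.94 | 50/59 = 0.85 |
| 60 s | 80/86 = 0.93 | 80/98 = 0.82 |

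Duty cycle thus falls by 3 to 7% or by 9 to 18% with gate-keeping unchanged. The reverse also holds: with q = 1, cutting rest from 40 s to 30 s moves D from 20/60 = 0.33 to 20/50 = 0.40, a 20% rise.

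**Rest increase that cancels a real gain.** Setting the two duty cycles equal gives H + R1 = (q1/q0)(H + R0). For q rising from 0.70 to 0.80:

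- R0 = 10 s: (0.80/0.70) × 30 − 20 = 14.3 s, 43% longer
- R0 = 30 s: (0.80/0.70) × 50 − 20 = 37.1 s, 24% longer
- R0 = 60 s: (0.80/0.70) × 80 − 20 = 71.4 s, 19% longer

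**Simulation.** There were 1,000 runs per scenario, with 25 patients. q was uniform on 0.60 to 0.85 with SD 0.05 noise per condition. Rest was uniform on 10 to 60 s with SD 0.15 noise on the log scale. Tests were two-sided at 0.05.

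| True gain in q; rest with goggles | Duty cycle, signed-rank: goggles better / worse | In-window fraction, signed-rank: significant | Duty cycle, rank sum: significant |
|---|---|---|---|
| 0; equal | 2.1% / 2.9% | 4.5% | 0.0% |
| 0; 30% longer | 0.0% / 99.3% | 5.8% | 29.9% |
| 0.10; equal | 97.5% / 0.0% | 100% | 10.2% |
| 0.05; equal | 51.5% / 0.0% | 90.7% | 0.1% |
| 0.10; 30% longer | 0.3% / 13.8% | 100% | 0.0% |

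Goggles are optional, so fewer patients may contribute. With 15, the second row gives 93.1% wrongly worse, and the fourth gives 32.0% for duty cycle against 70.0% for the in-window fraction.

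**Reading.** With equal rests the paired test on duty cycle is valid (2.1% + 2.9% = 5.0% false positives) but noisier. With unequal rests it is biased. Under the rank sum test, between-patient differences in rest stay in the comparison, and power for a gain of 0.10 drops from 97.5% to 10.2%.

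**The case against.** The strongest reply is that the documents never say the time base includes rest. Section 1.0's gloss of beam-on time would contain none. This stands: rest in the denominator is an inference from Section 12.0's description and the recorded interval. The gloss does not rescue the measure, though. The beam is held when the target leaves the window, so beam-on time alone cannot show time spent outside it.

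Second, a reader might infer that a perfect breath-holder with long rests is ranked below a poor one with short rests. The signed-rank test in Section 14.0 compares each patient with himself or herself, so a stable resting habit largely cancels. That ranking matters only under the rank sum test of Section 12.0.

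Third, initial goggle practice, couch set-up, planned cone-beam imaging and repositioning come before first beam-on (Sections 9.1 and 9.2). Some set-up corrections and extra images during treatment follow a target leaving tolerance or failed attempts, so they do bear on gate-keeping. This stands, and it leaves recovery breathing as the main non-hold component.

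Fourth, Section 12.0 also plans to look at interruptions, beam holds, DIBH attempts and staying within tolerance, and Section 14.0 tests interruptions under the first secondary objective. Duty cycle is therefore not the only evidence on goggles. It remains the only formal test named for this objective.

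Last, an in-window fraction has its own blind spot. A patient who releases after 5 s in the window scores 5/5 = 1.00, the same as a full 20 s hold at 20/20. This also stands, and the fix allows for it.

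**Conclusion.** The point holds in a limited form. The objective concerns gate maintenance, while its only formal test uses a delivery-time measure with no stated numerator or denominator. On the most natural reading that measure mixes in rest and other non-hold time.

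A reader might go further and conclude that the planned test gives the wrong answer. The documents do not support that. Bias requires non-hold time to differ between a patient's goggle and no-goggle fractions. This is possible without randomization, but no section says it happens, and its size is unknown. The 99.3% and 0.3% figures follow from an assumed 30% difference in rest. With equal rests the paired test keeps its error rate, and the cost is noise: 51.5% against 90.7% power for an assumed gain of 0.05.

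The conflict between the rank sum and signed-rank tests needs no assumption and should be resolved. Overall this is an improvement to consider. Section 4.1 presents the secondary objectives as exploratory, no power or decision rule is attached to this comparison, and the primary feasibility analysis is unaffected.

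**What to change.** In Sections 12.0 and 14.0, for the second secondary objective:

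1. Test gate maintenance with a measure from the recorded Calypso traces: seconds inside the assigned window divided by seconds of active breath-hold. Mark hold start and release by a fixed rule written in advance.
2. Report in-window seconds per breath-hold attempt beside it, so that early release is visible.
3. Average within patient and condition, then apply the signed-rank test already planned in Section 14.0. Change the rank sum test in Section 12.0 to match.
4. Keep duty cycle as a separate delivery-efficiency measure, with its numerator, denominator and exclusions stated once and used consistently. Reconcile the doubling in Section 1.0 with the halving in Section 12.0.

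The cost is protocol and SAP wording plus trace processing. No new patients or measurements are needed. The main burden is agreeing and applying the rule for hold start and release.
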